PROTOCOL FOR PIVOT PILOT STUDY:
PATIENT INFORMATION VIDEOS ON OPERATIONS TRIAL

SUMMARY

Patient education is an important part of preparing patients for surgical procedures. This pilot project aims to determine the use of two educational videos created by specialists for patients due to have either an elective caesarean section or a trans-vaginal tape / trans-obturator tape. This pilot study aims to gather the information required to undertake a larger scale study which will assess whether there is a relationship between preoperative anxiety levels and education on the procedure when the educational video is used as an information giving tool alongside existing resources. A total of 120 patients will be enrolled (60 per group) and randomised to either watch the video or not watch the video. Assessment will be done by means of a questionnaire, and results will be collected over the course of eight months. It is expected that the video may reduce anxiety in preoperative patients and that they may feel better informed about the reason for the operation, the procedure and the post-operative period.

RESEARCH QUESTION

Does the additional use of multimedia provide a more effective means of educating the patient on risks and benefits of a common elective surgical procedure as well as reduce overall pre-operative anxiety?

RATIONALE & BACKGROUND INCLUDING LITERATURE REVIEW

While patients are always explained the key risks and complications of any elective surgical intervention, they often feel unprepared for both the hospital stay and the postoperative period.^{1,2} Multimedia has already been used in randomised trials as a means of delivering information to patients preoperatively to reduce overall anxiety regarding the procedure.^{2,3,4}

Currently in the NHS patient information regarding surgical procedures is delivered through tools such as leaflets in combination with consultations where the patient is able to ask questions. A video is a concise learning tool which the patient would be able to access 24/7 and also show their relatives. This would not only allow them enough time to think through the possible complications but also to inform them of accurate and up to date information which is included in the consent forms they are presented pre-operatively.

A learning needs assessment where patients were approached post-operatively in Royal Devon and Exeter Trust, Wonford Hospital and asked to complete a questionnaire regarding pre-operative knowledge and anxiety highlighted certain points which patients felt they would have liked to have been informed of sooner. For example patients who had undergone a C-section commented that side effects of the anaesthetic were not fully explained and therefore not expected, and this was subsequently included in the video for this patient group. Other comments from the TVT/TOT post-operative patients involved a request for a detailed explanation of urinary incontinence and treatment options, including recovery time. Every effort was made to include the feedback from patients as points to cover in the educational videos created.

This study aims to highlight the benefit of provision of a cheap and accurate information tool in the form of a video designed to complement existing methods of preparing patients for elective surgical admissions. The ultimate goal is to prepare a database of a selection of videos accessible to patients in their own home at any time. The videos will be

monitored and updated, and any videos submitted to the website will be assessed by two specialist consultants for accuracy prior to being added to the database.

AIMS AND OBJECTIVES

Aim: Determine whether educational videos are of use as an additional learning resource for pre-operative patients.

Objectives:

- 1- Quantify the change between baseline patient anxiety and operative knowledge at preoperative assessment, compared to immediately pre-operatively in intervention and control group.
- 2- Record the relative change in anxiety level of pre-operative consented patients who have seen the video to those who have not using a ten point visual analogue scale and the State Trait Anxiety Inventory.
- 3- Record the relative change in knowledge base of pre-operative consented patients who have seen the video to those who have not. Specifically these headings will be assessed:
 - The condition
 - The operation
 - The risks and complications
 - The post-operative period

Secondary Objectives:

- 1- Receive verbal and written feedback on the videos in order to improve them
- 2- Test data collection methods, especially questionnaires.
- 3- Assess recruitment rate
- 4- Test the delivery of the video
- 5- Get an estimate of standard deviation of the outcome measures.
- 6- Get an estimate of required resources for a full randomised control study.

PLAN OF INVESTIGATION

General research design: A pilot randomised controlled study

Randomisation will be secured through the use of opaque envelopes for allocation to study arm. Block randomisation of 10 participants will be used in order to keep the sizes of treatment groups similar. The co-investigator will organise the blocks of envelopes and distribute these to the sub-investigators.

The questionnaires for knowledge will contain a linear scale representing two extremes with patients deciding where they lie on the scale by choosing a numerical value, and the answers will be allocated to a point scoring system for quantitative analysis.

The assessor will be blinded to the allocation during data input.

The study analysis will be performed by a member of the team who will be blinded to patient allocation.

Study Population

Target population: Stage 1 (baseline anxiety and knowledge): Preoperative assessment patients who have been consented for the study. Stage 2: Pre-operative patients who have been consented for their operation and for the study, in the Royal Devon and Exeter Trust, Wonford Hospital

Operations: Elective Caesarean Section, Trans-Vaginal/Trans-Obturator Tape

Age range: Minimum 18 years of age. No maximum age

Ethnicity: Any

Inclusion criteria:

- Patients due to have one of the following operations: Elective Caesarean Section, Trans-Vaginal / Trans-Obturator Tape
- Patients must be consented for the operation before participating in stage 2 of the study.
- English speaking

Exclusion criteria:

- Any conditions which may affect capacity: eg dementia, previous CVE or reduced cognitive ability

Mechanism of Selection and Recruitment:

Eligible patients will be approached by their clinician or nurse within the direct care team during consultation and the project will be explained to them. Verbal consent will be obtained to provide the patient with a Patient Information Sheet (see appendices)

Three weeks before the operation, either a research nurse or research midwife will telephone the patient and obtain verbal consent for participation in the study, explaining the project and answering any questions. This will be recorded in the notes. If consent is not obtained, it will be recorded in the notes that the project was explained and the patient is not willing to take part. If consent is gained, the patient will be seen during preoperative assessment by the research nurse or midwife to obtain written consent. Two copies of the completed consent form will be made (1 (original copy): to be filed for study data, 2: to be given to the patient, 3: to be inserted into medical notes). The patient will then be asked to complete Questionnaire 1.

On the day the patient is admitted to hospital for their operation, the patient will be approached by the research nurse or research midwife, who will confirm the patient is still happy to take part in the study. If the patient gives continued consent, the patient will then be allocated the intervention or control group as per opaque envelope allocation. This will then be marked on the consent form appropriately. The research nurse or research midwife will then double check the allocation number matches on each of the following forms: Consent form, Questionnaire 1, Questionnaire 2.

If the patient is allocated the intervention group, the video will be shown through use of a laptop or ipad, with earphones or in a private room. The patient will then be asked to complete Questionnaire 2. If control group is allocated, then no video will be shown, and the patient will be asked to complete Questionnaire 2.

No questions regarding the video or operation will be answered by the research nurse or research midwife until after completion of Questionnaire 2 during phase 2 of the study.

Potentially eligible patients within 8 months:

- Elective Caesarean section: 120 (4 patients per week with no recruitment during holiday periods). 60 patients per arm could potentially be approached.
- TVT/TOT: 150 (5 patients per week with no recruitment during holiday periods). 75 patients per arm could potentially be approached.

Of these, an estimated 3/10 will not accept to take part, or will be lost to follow up (drop out at stage 2 of the project). Sub-investigators may not be available for each of the operating

lists.

Target number of total patients to enrol in pilot study:

- Elective Caesarean section: 60 in total. 30 patients per arm
- TVT/TOT: 60 in total. 30 patients per arm.

Interventions

- Elective Caesarean section:
Intervention: 'C-Section Video' shown on a laptop. It will run through once only.
Control: No video

- TVT/TOT:
Intervention: 'TVT/TOT Video' shown on a laptop. It will run through once only.
Control: No video

Adverse events/patient safety

No issues of patient safety should arise. An adverse event would be if the video caused undue additional anxiety due to a question the patient may have after watching it.

- The videos will be presented to the communications manager of the RD&E trust for approval prior to showing them to the patients.
- Should the patient have any further questions due to watching the video, having completed the questionnaires, it will be ensured that either a nurse or a doctor can answer these before the operation.

Any adverse event will be appropriately logged and submitted to the Research and Development department quarterly, if required.

Data collection and outcome measures:

Data will be collected by two delegates (sub-investigators: research nurse or research midwife).

The data will be collected in the form of written questionnaires – see appendices for drafts.

Stage 1: Gaining consent and Baseline assessment:

- 1) Consent forms and questionnaires will be grouped according to operative procedure, and numbered consecutively: 001-120.
(001-060: TVT/TOT, 061-120: ELECTIVE CAESAREAN SECTION)
- 2) Potential patients will be given the Patient Information sheet by a member of their direct care team during clinic.
- 3) Three weeks before their operation, the patient will be telephoned by the research nurse or midwife, the project explained to them, and verbal consent will be gained for study participation.
- 4) Patients who have given verbal consent for participation will be seen during preassessment and the patient will be asked to complete the written consent form and questionnaire 1.
- 5) On arrival at the hospital for their operation, the patients will be approached by the research nurse or research midwife to confirm consent and continue with phase 2 of the study:

Stage 2: Allocation and re-assessment

- 6) When the patient arrives for her operation, the research nurse or midwife will

approach the patient, and verbally confirm that she is still happy to continue with the project.

- 7) The research nurse will ensure allocation number matches on all documents, including questionnaire 2.
- 8) The patient will be asked to complete the second consent form that will then be inserted into the medical notes.
- 9) The research nurse will open an opaque envelope to view allocation of patient
- 10) If intervention:
 - a) The research nurse will give the laptop to the patient with the video to play. No comments are made regarding the operative procedure etc.
 - b) The research nurse marks the intervention box on the consent form.
 - c) The research nurse ensures the patient name matches the consent form, and the number on the consent form matches the number on 'Questionnaire 2'.
 - d) Following the viewing of the video, the research nurse presents 'Questionnaire 2' to the patient.
 - e) The questionnaire will be collected and filed into the wallet with other questionnaires for that operative procedure group.

10) If control:

- a) The research nurse marks the control box on the consent form.
- b) The research nurse ensures the patient name matches the consent form, and the number on the consent form matches the number on 'Questionnaire 2'.
- c) The research nurse presents the 'Questionnaire 2' to the patient.
- d) The questionnaires will be collected and filed into the wallet with other questionnaires for that operative procedure group.

Stage 3: Data Analysis

1. Data analysis: The co-investigator will be given the wallets with the questionnaires and assimilate the data in an excel sheet, recording the participant number alongside the results.
2. Once all the data has been entered, the co-investigator will send the Excel sheet to the chief investigator as the initial stage of analysis, and date and sign it.
3. Then the co-investigator will open the wallet containing the consent forms and record the allocation next to the participant number, and regroup the data.
4. The data will then be sent to the statistician in order to proceed to statistical analysis.

Note on Blinding:

As the participant number and the subsequent allocation will be completely random as per point 8), the initial stage of the data assimilation onto the Excel sheet will be performed blindly as the co-investigator will not know which participant number corresponds to which study arm. As this document will then be sent to the chief investigator this prevents the data from being altered once the allocation is viewed in the second stage (Stage 3, point 1,2).

Data management and statistical analysis

Patient consent forms and questionnaires will be filed securely in a padlock protected

locker at the Research and Development Building, Wonford.

No patient identifiers will be recorded on home laptops or home computers.

The data will be assimilated in an Excel Sheet and stored on a password protected computer/laptop.

Consent forms will be held for 3-6 months and then destroyed.

Additional data will be held for 5 years.

All Data Protection guidelines and the Data Protection act will be adhered to for confidentiality purposes.

The trust statistician will be approached for advice on randomisation of the opaque envelopes.

The person who undertakes the role of randomisation will be recorded in the research study log.

Descriptive statistics of baseline characteristics will be compared between study groups to demonstrate the effectiveness of randomisation. Categorical data will be summarised as proportions and percentages as appropriate with associated confidence intervals. No attempt will be made at this stage to make formal comparisons of outcome measures – this will be done in the eventual definitive study. Summaries of secondary outcome measures will also be produced in a similar manner to the above.

PROJECT MANAGEMENT

Personnel

Producing the video:

Animator: Consultant Anaesthetist

Producer and Voiceover: Consultant Obstetrician & Gynaecologist

Camerawoman and Editor: Communications and Corporate Affairs Officer

Writer, Director and Researcher, Creation of Storyboards: Year 5 Intercalating Medical Student (2011/12)

Quality Control: Trust Communications Manager

The Study

There will be four delegates:

Chief Investigator: Consultant Obstetrician & Gynaecologist.

Co-Investigator: Foundation Year 1 Doctor, RD&E (2013-14)

2x Sub-Investigators: Until December 2012: Clinical Medical Student and Foundation doctor

From July 2013: Research nurse and research midwife

Statistician: Hospital Trust Statistician

Project Responsibilities:

Data storage/monitoring: Sub-Investigators

Consenting: Sub-Investigators

Recruitment: Sub-Investigators

Statistical advice: Hospital Trust Statistician

Data analysis: Co-investigator

Write-up: Co-investigator and Chief Investigator

Additional Training Required: For the Sub-Investigators, if not already obtained, GCP Training will be required.

*First Main Contact for the Study: [name], Foundation Year 1 Doctor, RD&E.
[contact], [name]*

Time-scheduleStart date: 31st August 2011

Month	1 (Sep)	2	3	4	5 (Jan) 2012	6	7	April 2012 – June 2013 Recruitment delay and re- evaluation	11 (Jul) 2013	12	13	14	15	16	17 (Jan) 2014)	18	19	20	21	22	23	24 (Aug) 2014)	
Create Videos	x	x																					
Protocol Submission		x			x																		
Ethics Submission					x																		
Delegate recruitment						x																	
Patient Enrolment*							x	x	x	x	x	x	x	x	x	x	x	x	x	x	x		
Research staff recruitment									x														
Data Entry										x		x		x		x		x	x	x			
Data Analysis and write-up																					x	x	x

*Should the necessary minimum number of patients required be recruited before month 13 then patient enrolment will cease accordingly.

Day-to-day study management

Day to day management will be ensured by the Co-investigator, Foundation Year 1 Doctor. Additional delegates recruited, if not GCP trained, will be notified to the Research department and be registered for a training day.

ETHICAL CONSIDERATIONS

An Integrated Research Application System Form is being completed for ethics approval. Written consent will be gained from patients for participation. See appendices

Confidentiality:

- Questionnaires will not contain any patient details other than demographic information.
- Questionnaires will record participant number, which will be recorded with the consent form.
- One original consent form will be collected and two copies of the complete form will be made. One will be filed securely with co-investigator, one will be given to the patient, and the other inserted into medical notes.
- Documents containing patient identifiers will be held for 3-6 months from study end and then shredded.
- All other documentation will be held for 5 years.

Any queries patients may have regarding the study will be answered by the research team (Delegate A or B) prior to obtaining consent during Stage 1 of the study.

Participants willing to receive a copy of the study findings will indicate this in the consent form. These patients will be sent the information within 6 months of study end.

BUDGET SUMMARY AND COSTINGS

Please see separate budget listing.

Funding of £250 has been obtained through the May Sullivan Research Prize towards costs of the project.

A small grants application (R&D) will be made once protocol has been accepted.

POSSIBLE IMPLICATIONS OF STUDY

The results from the study will be entered into the following:

1) Conferences for presentation:

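### The plan promises a blinded analysis, but Stage 3 attaches the allocation before the data go for analysis with no masking step described, and it is unclear who the analyst is

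*Combined protocol and SAP*

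**What the plan says.** The General research design text makes two separate blinding commitments. One is that the assessor does not know the allocation while data are being input. The other concerns the analysis itself: "The study analysis will be performed by a member of the team who will be blinded to patient allocation".

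Stage 3: Data Analysis sets out the procedure in four items.

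- Item 1: "The co-investigator will be given the wallets with the questionnaires", and that person enters the results in Excel by participant number.
- Item 2: "the co-investigator will send the Excel sheet to the chief investigator as the initial stage of analysis, and date and sign it".
- Item 3: the co-investigator is then to "open the wallet containing the consent forms and record the allocation next to the participant number, and regroup the data".
- Item 4: "The data will then be sent to the statistician in order to proceed to statistical analysis".

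The Note on Blinding that follows explains why the first stage of data entry is blind, and why a sheet already sent to the chief investigator cannot be altered once the arms are known. It says nothing about the analysis.

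Project Responsibilities lists "Data analysis: Co-investigator" and, separately, "Statistical advice: Hospital Trust Statistician".

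**The concern.** A blinded analysis needs some point at which the analyst is kept from knowing which group is which. In Stage 3 the last action before the data reach the statistician is the opposite: the true arm, ticked as intervention or control on the consent form, is written next to each participant number. No later item turns it into a code.

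The promise also cannot be checked against a person. If the analyst is the co-investigator, as Project Responsibilities can be read, the same person has just recorded every allocation.

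What is at stake is mainly the accuracy of the eventual report. Objectives 1 to 3 call for change in anxiety and knowledge by arm, so by-arm results will be produced even without formal tests. Some choices remain open when those summaries are made. For example, the protocol mentions a point-scoring system for the knowledge questions, but the section on statistical analysis does not set it out. Blinding the analyst protects choices of that kind. The pilot is also meant to inform a larger study, which could inherit the same gap.

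**Working it through.** No arithmetic decides this point. The check sets the blinding statements against the steps that would have to deliver them.

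**1. What is promised.** There are three blinding statements: data input (General research design), analysis (General research design) and the Note on Blinding (after Stage 3). The first and third concern data entry. Only the second concerns analysis. Because data input and analysis are promised in separate sentences, the second cannot be read as a restatement of the first.

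**2. What supports blinded data entry.** Items 1 to 3 are in the right order: questionnaires first, signed sheet to the chief investigator second, consent forms opened third. The Confidentiality section adds "Questionnaires will not contain any patient details other than demographic information", with only a participant number as the link. One condition is left open. The General research design text has the co-investigator, who enters the data, also organise and distribute the blocks of envelopes. The plan does not say whether that person could link envelopes to participant numbers.

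**3. What supports blinded analysis.** The allocation is attached at item 3 and the data are sent at item 4, with nothing between them. Neither item mentions coded labels, a withheld key or a masked file. The Note does not extend to this stage.

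**4. Who the analyst is, and what follows.**

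- *Co-investigator* (one reading of Project Responsibilities): this person recorded the arm of every participant at item 3. With the planned enrolment that is 2 procedures × 2 arms × 30 = 120 participants. The analysis is unblinded.
- *Statistician* (Stage 3, item 4): the file arrives after allocations have been recorded and the data regrouped. The analysis is blinded only if the groups were relabelled on the way, which the plan neither describes nor excludes. The Data management section adds that the trust statistician will be approached for advice on randomising the envelopes, without saying whether that gives access to the sequence.

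**5. Result.** On the first reading the promise fails. On the second it depends on an unwritten step.

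**The case against.** The strongest reply is that silence is not failure. Recording the allocation and regrouping the data does not rule out sending groups under neutral labels, and the protocol itself says that the analyst will be blinded. This stands in part. A reader might infer that the statistician will certainly see named arms for all 120 participants; the document does not support that. It supports only that masking is not described, and a safeguard that is not written down cannot be followed consistently or audited.

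A second reply concerns the analyst. Item 1 of Stage 3, which is data assimilation by the co-investigator, carries the label data analysis, and item 2 calls the resulting sheet an initial stage of analysis. The entry in Project Responsibilities may mean that task, with statistical analysis left to the statistician at item 4. This is a fair reading, so a proven contradiction over who analyses should not be inferred. Ambiguity remains, because the same list gives the statistician advice only, and the General research design text treats data input and analysis as different things.

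Third, this is a pilot. Patients complete the scales themselves, the Data management section rules out formal outcome comparisons at this stage, and the entered values are lodged with the chief investigator before the arms are seen. All of this stands, and it is why the point is minor.

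A reader might also go further and infer that blinded data entry fails, because the co-investigator organises the envelopes. The document does not show that this person can link an envelope to a participant number; it leaves the matter unstated. Nor should anything be built on the cross-reference to point 8 in the Note on Blinding, which is clerical, or on which consent form bears the arm mark, which cannot be judged without the forms themselves.

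**Conclusion.** The concern holds in a limited form. The protocol promises an analysis blinded to allocation, and the written procedure does not provide it: allocation is attached immediately before the data leave for analysis, no masking is described, and the analyst is not clearly identified. If the co-investigator analyses, the analysis is unblinded. If the statistician does, its blinding is undetermined.

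Any resulting bias cannot be calculated from the document. It is expected to be small, given self-completed scales and descriptive summaries. The practical consequence is that a report repeating the protocol sentence would claim a safeguard the procedure does not contain. Severity is minor.

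This rests on two assumptions: that Stage 3 is the full procedure for handling data before analysis, and that the promise was meant to cover the by-arm summaries of anxiety and knowledge.

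**What to change.** 1. State in the General research design text, Stage 3 and Project Responsibilities that the statistician carries out the outcome analysis, and describe the co-investigator's role as data entry and coding.

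2. Reword Stage 3 item 3 so that, once the signed sheet is with the chief investigator, the arms are attached as codes A and B. Withhold the key from the statistician until the summary tables are final. Keep out of that file any data only video patients could supply, such as feedback on the video if it is recorded per participant: with two codes, one such record reveals both. Planned arms are equal (30 and 30 within each procedure), so group size should not give the code away.

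3. State who may hold a list linking participant numbers to arms, and when. The co-investigator, who organises the envelopes and enters the data, should hold none until the signed sheet is lodged. The statistician, who may advise on randomisation, should hold none until the tables are final.

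4. If this is not adopted, limit the blinding statement in the General research design text to data input. That alone removes the mismatch.

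The cost is some rewording and a little coding work at item 3, with no extra patients, visits or staff. One weakness remains: a large difference between the codes could still let the statistician guess the arms.

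### The one adverse event the plan names covers only question-triggered anxiety attributed to the video, so the harm log omits content-related worsening and gives no count comparable across arms

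*Combined protocol and SAP*

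**What the plan says.** The section Adverse events/patient safety opens with the expectation that "No issues of patient safety should arise" and then names a single event: "An adverse event would be if the video caused undue additional anxiety due to a question the patient may have after watching it". It gives no threshold for what counts as undue, no procedure for eliciting the event, and no summary by arm. On reporting it says: "Any adverse event will be appropriately logged and submitted to the Research and Development department quarterly, if required".

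Anxiety is also an outcome. Objective 1 asks for the change in anxiety from preoperative assessment, "compared to immediately pre-operatively in intervention and control group". Objective 2 asks for the relative change in patients who have and have not seen the video, "using a ten point visual analogue scale and the State Trait Anxiety Inventory". The second measurement is taken in both arms. In the video arm, "Following the viewing of the video, the research nurse presents 'Questionnaire 2' to the patient"; for controls, "If control group is allocated, then no video will be shown, and the patient will be asked to complete Questionnaire 2". In neither arm does the research nurse or midwife answer questions before that form is complete: "No questions regarding the video or operation will be answered by the research nurse or research midwife until after completion of Questionnaire 2".

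The section Data management and statistical analysis provides for proportions and percentages with confidence intervals for categorical data. It defers formal comparison of outcome measures to the definitive study.

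**The concern.** The definition is narrow in three ways.

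- **Trigger.** A patient who becomes more anxious simply from seeing the operation or its complications described, with no question arising, falls outside it.
- **Comparator.** An event that the video must have caused cannot occur in patients who were not shown it.
- **Attribution.** Someone must judge, for one patient on the day of surgery, that the video was the cause. Anxiety may rise by then in either arm, since the first questionnaire is completed at preoperative assessment (its heading says about three weeks before the operation). The research nurse who opens the envelope and hands over the laptop also knows the allocation.

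The video is meant to lower anxiety, and the pilot is meant to inform a larger trial. The share of patients who become more anxious is therefore useful to know. The scores that would show it are planned in both arms, but the plan neither links them to its harm definition nor says that patients who worsen will be counted.

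**Working it through.** **Inputs from the documents.** There are two procedures with 30 patients per arm in each: 2 × 2 × 30 = 120, which reproduces the stated total. That is 60 per arm with procedures pooled. No rate of worsening and no standard deviation is given; estimating the latter is a secondary objective. The rates below are assumptions, and complete data are assumed throughout.

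**Step 1: what each source of information can show.**

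| | Video arm | Control arm |
|---|---|---|
| Named adverse event, question-triggered anxiety | Can occur | Zero by construction |
| Anxiety from content, no question | Outside the definition | Not applicable |
| Rise in anxiety score, any cause | Measured | Measured |

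Only the last row gives a comparison between randomised groups.

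**Step 2: why a count in one arm is hard to interpret.** Suppose 20% of patients worsen by the day of surgery whatever their arm. Then 0.20 × 60 = 12 video patients worsen with no video effect at all. Nothing in a log confined to events attributed to the video separates these 12 from patients harmed by it.

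**Step 3: what the planned mean change can show.** The 95% half-width for a between-arm difference in means is 1.96 × √(2/n) standard deviations:

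- n = 60: 0.36 SD
- n = 30: 0.51 SD

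A mean worsening could therefore be estimated, though imprecisely. A mean can still conceal a subgroup. If 20% rise by 3 points and 80% fall by 1, the mean change is 0.20 × 3 − 0.80 × 1 = −0.2, an apparent slight improvement with one patient in five worse by 3 points. These values are illustrative.

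**Step 4: precision of a count of patients who worsen.** At a common rate p, the 95% half-width for one arm is 1.96 × √(p(1−p)/n), and for the difference 1.96 × √(2p(1−p)/n). At p = 0.20:

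- one arm: 1.96 × √(0.16/60) = 10 points; 1.96 × √(0.16/30) = 14 points
- difference: 1.96 × √(0.32/60) = 14 points; 1.96 × √(0.32/30) = 20 points

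Over a range of assumed rates, the half-width for the difference is:

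| Assumed rate in both arms | 60 per arm | 30 per arm |
|---|---|---|
| 10% | ±11 points | ±15 points |
| 20% | ±14 points | ±20 points |
| 40% | ±18 points | ±25 points |

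With an assumed 20% in controls and 40% in the video arm, the difference of 20 points would have a 95% interval of 4 to 36 at 60 per arm and −3 to 43 at 30 per arm.

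**Step 5: what an empty log would mean.** With no events in n patients, the one-sided 95% upper limit is 1 − 0.05^(1/n): 4.9% for n = 60 and 9.5% for n = 30. These limits come from the sample size alone and would not change with rewording. They show only that a clean log is weak reassurance.

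**The case against.** The strongest reply is that the log is an operational reporting tool. Nothing in the plan says that its counts will be analysed or used to judge harm, and an event attributed to an intervention naturally has no control counterpart. That is fair. It is why the remedy lies mainly in the outcome summaries. It does not explain why the definition should exclude anxiety caused by the content.

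A reader might infer that the pilot cannot show whether the video worsens anxiety. The documents do not support that. Objectives 1 and 2 record change on two anxiety measures in both randomised arms, the change can go in either direction, and the adverse event wording places no limit on those data. Inference is limited by the pilot's size and by its deliberate choice not to compare outcomes formally.

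A reader might also infer that adverse events are logged in the video arm only. The reporting sentence covers any adverse event, without restriction by arm. What is missing is a defined event that a control patient could have.

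A further objection is that a between-arm difference with an interval comes close to the formal comparison that the plan defers. This stands in part: the core of the table should be the proportion in each arm with its own interval, which the plan already allows for categorical data.

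Finally, the questionnaire pages available to this review show knowledge items and no anxiety items. Pages appear to be missing from the extract, so nothing is concluded from this. The proposal relies on the objectives as stated.

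**Conclusion.** The point holds as a minor gap in how harm is captured and summarised; it is not a design failure. The named adverse event omits content-related worsening, rests on bedside attribution by staff who know the allocation, and gives no count that can be set against controls. Average worsening would be visible in the by-arm anxiety change. The number of patients who worsen would not be visible in any summary that the plan states.

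The scale is modest. A two-arm count would carry about ±14 percentage points on the difference with procedures pooled and ±20 within one procedure, on an assumed 20% rate in both arms and complete data. That suits description and planning of the larger trial; it would not settle whether the video does harm.

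**What to change.** 1. In Adverse events/patient safety, delete the words that make a patient's question the trigger, so that anxiety caused by the video's content is not excluded. The arrangements for answering patients' questions stay as planned.
2. In Data management and statistical analysis, add one descriptive table by arm, pooled and by procedure. It gives the number and proportion of patients whose anxiety rises from Questionnaire 1 to Questionnaire 2, irrespective of cause, on the ten-point scale and on the State Trait Anxiety Inventory, with a 95% confidence interval for each arm.
3. Fix the cut-offs before allocation is linked to the scores. Rises of at least 1, 2 and 3 points on the ten-point scale are one possibility; the documents give no basis for a particular choice. State cut-offs for the inventory as well.
4. If a between-arm difference is shown, label it descriptive and report no test, in keeping with the plan's decision to leave formal comparison to the definitive study.

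The cost is a few words of protocol text and one table from scores that the objectives already call for, with no extra patients or visits. The drawback is wide intervals, above all by procedure, and several cut-offs that should not be searched for the most striking result.
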